2. The current study will be a randomized single-blinded placebo-controlled phase III clinical trial for this Investigational new device (SQ53 wipes) intended for the catheter cleaning in patients receiving home parenteral nutrition.
3. With ethanol lock therapy being phased out, there is no currently approved effective and readily available modality available in the United States to prevent CRBSI. On compassionate grounds it is imperative to use and to study SQ53 so that patients can benefit from this clinical trial.

Study design: Prospective randomized single-blinded placebo-controlled clinical trial

*Please note that the randomization will also be stratified by PICC/Tunneled catheter type.

Study objectives:

Primary objective:

1. To determine the effectiveness of SQ53 wipes in prevention of CRBSI in patients receiving home parenteral nutrition.

Secondary objectives:

1. To identify if there are any major or minor adverse effects such as skin irritation associated with the use of SQ53 wipes.

Inclusion criteria and patient recruitment:

1. Adult (age>18) patients requiring home parenteral nutrition support via PICC line or tunneled CVC.
2. Patients will be included via following process:
 - a. All patients managed by CCF HPN team, meeting the inclusion criteria will be sent a letter of information and full informed consent form.
 - i. Letter of information will be a cover letter informing patients about the clinical trial (letter attached)
 - ii. Informed consent form: Standard informed consent form with detailed information about the study as per the Cleveland Clinic guidelines.
 - iii. Letters will be sent in an alphabetical order for 10-15 patients each week to evenly distribute the work burden overtime.
 - b. Patients who are interested to enroll in the study will call our HPN team, and we will answer any questions that these patients might have.
 - i. The consent form will be again sent via email.
 - ii. HPN dietitian will take consent over the phone by using DocuSign and will document it in patient's chart in HPN database
 - iii. HPN dietitian will notify caring NST physician regarding patient's enrollment in the trial.

- c. HPN dietitian (or NST physician or both) will classify patient in either a High Risk, Low Risk or New Patient Category via specific criteria.
 - i. **Identification of high-risk patients** which will be determined by the following criteria:
 - 1. History of one or more CRBSI infection in the past 6 months

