 - 2. Immunocompromised state increasing the infection risk
 - a. Clinical determination based on comorbidities such as HIV, immunosuppressant medications, and steroids (prednisone >40mg per day)
 - 3. History of multiple catheter exchange in the past (greater or equal to 2 within the past 6 months) with difficult access
 - a. This determination to be made based on patient's history
 - ii. Identification of Low risk patients:
 - 1. Patients who do not meet High-risk criteria will be classified as Low risk patients
 - iii. New patients:
 - 1. New patients are the patients who are newly started on PN during their in-patient stay and those who have been on PN less than 6 months unless they had CRBSI in the time frame.
 - 2. These patients will receive information about the clinical trial by RNs who provide education as standard of care.
- d. Patients can also be enrolled in the study at the time of outpatient visit, or before discharge from the hospital.
- 3. Cleveland Clinic Home Infusion Pharmacy (CCHIP) will be informed about patient's enrollment and the risk category (High vs Low vs New patient) and the catheter type (PICC or tunneled)
 - a. CCHIP will perform stratified randomization and assign the patient to either Treatment (SQ53) or PLACEBO (Alcohol wipes) group.
- 4. Treatment group will also have the SQ53 impregnated wipe used on a remote site to check for hypersensitivity and any other skin reactions before it is deemed safe to use routinely in that patient.

5. All enrolled patient will need to agree to reach out to Home Nutrition Pager which is available 24x7 in case of noted adverse effect – this is standard of care for home PN patients.

Exclusion criteria:

1. Age less than 18 years
2. Women known to be pregnant (patient will be asked verbally- no pregnancy test will be performed)
3. Women of childbearing age who are planning a pregnancy
4. Women who are breastfeeding
5. Patient's refusal to enroll in the study at any point in time
6. Patients who refuse to use disinfectant wipes daily.
7. Patients who use port for their PN infusion.
8. Patients who are enrolled in other clinical trials with investigational drugs or device

Blinding and Randomization:

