- **Blinding:** This will be a single blinded study and the NST-providers will be blinded to the treatment arm that the patient is assigned to. A clinician will initially interview the patient and at the time of enrollment into the clinical trial, obtain an informed consent after which the patient will be enrolled in the study.
- **Blinding the patients is not possible** due to several reasons:
 - o SQ53 and alcohol wipes will have labels on them
 - o differences in physical characteristics (smell) which are distinct for alcohol wipes and SQ53
 - o therefore, it is unfeasible to blind patients to the intervention.
- **However,** despite being an unblinded study, outcome of our study is not likely to be affected as the primary outcome measure is diagnosis of CRBSI which is based on the Positive Blood Culture and is not very likely to be impacted by a placebo effect.
- **Randomization with a placebo:** Once patients are enrolled into our study, patient's information will be discussed with the pharmacy who will assign the patient to either a treatment or a placebo group.

- Patients will be randomized in 1:1 ratio to receive either SQ53 or placebo. The randomization process will be stratified randomization, followed by blocked randomization in each stratum. Stratification will be done on two factors: CRBSI risk category and catheter type. CRBSI risk categories will be determined by the clinicians or NST staffs 1. High risk (1 or more CRBSI in previous 6 months) 2. Low risk (no CRBSI in previous 6 months) 3. New patient. Catheter types will be 1. Tunneled central catheters 2. Non-tunneled central catheters. The design has $3 \times 2 = 6$ strata. Blocked randomization will subsequently done in order to avoid serious imbalance in the number of participants assigned to treatment or placebo group. The block sizes will be determined by Cleveland Clinic Home Infusion Pharmacy.

Intervention:

Patients who qualify to enroll in the trial and sign an informed consent will be enrolled and will be eligible to receive either the intervention or the placebo. Providers will be blinded to which group patient is assigned to.

- Pharmacy (Cleveland Clinic Home Infusion Pharmacy will perform randomization and will assign patients to the groups)
- **All patients in the study will receive the wipes (Treatment group = SQ53 wipes, Placebo = alcohol wipes)**
 - o Provide packs of sterile wipes to the patient for daily use (**external use only**)

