 - o Wipes should be used daily, as well as, when the dressing is changed, by wiping the catheter surface and hubs for at least 15 seconds
 - o **Daily use:** Patients will be given instruction to clean the exterior and the caps of the intravenous catheters by following a sterile technique. This should be done before and after each use (i.e. PN infusion)
 - o **At the time of dressing change:** Standard practice is to change the dressing every week. At this time the patient will use wipes to clean the catheter exit site and skin around the catheter exit site, catheter exterior and catheter caps prior to applying the new dressing
 - o Wipes will be provided to the patient free of cost (material will be sponsored by the JVS company)

- Patients in both the groups will continue to use the standard care: i.e. ethanol (curos) caps, saline locks.

Data collection:

1. A registry of enrolled patients will be prepared. CCF HPN service has an approved database of patients receiving home parenteral nutrition. There are no additional HPI that will be collected as a part of enrollment in the study. The patient data is already collected into a password protected HPN database as current standard of practice. This data is routinely collected and updated by HPN dietitians.

Sample data sheet of primary objectives (data in *italics blue font* is for example):

Patient Nomenclature:				
SQ53/Treatment Group: Patient T1, Patient T2....				
Placebo Group: Patient C1, Patient C2....				
	Pre vs Post SQ53 trial enrollment	Number of Confirmed CRBSI in 6 months	Number of total admissions for CRBSI in 6 months	Number of catheters changed due to CRBSI in 6 months
Patient T1	Pre	2	3	0
	Post	0	1	0
Patient T2	Pre			
	Post			
Patient C1	Pre	0	1	0
	Post	1	1	1

Patient C2	Pre			
	Post			
Patient C3	Pre			
	Post			

Data protection, processing and, analysis of the data:

1. CCF HPN service has an approved database of patients receiving home parenteral nutrition. The patient data is already collected into a password protected HPN database as current standard of practice. We will use REDCap for data entry for analysis. All data will be password protected.
2. We plan to perform both "**Per Protocol**" and "**Intention to treat analysis**".

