3. Patients whose compliance is less than 90 percent will be excluded from Per Protocol analysis; however, those patients will be accounted in intention to treat analysis. Patients who developed skin reaction in remote site (e.g., forearm) will be excluded from Per Protocol analysis, but will be included in intention to treat analysis
 - a. Compliance will be determined by HPN dietitian at the time of phone/virtual visit encounters: patient will be asked about their disinfectant wipe use and compliance.
4. Our primary outcome measure (as listed in above data sheet) will be differences in the CRBSI rate at 6 months after patient enrollments into the trial (i.e. SQ53 use). We will also perform sub-analysis by utilizing patients as their own controls. Please see the detailed timeline below.
5. We will also analyze the differences in the number of admissions for CRBSI (which would include admission with suspect CRBSI), as well as, overall number of catheters changed for confirmed and suspected CRBSI.
6. We will perform Poisson Regression analysis to compare the rates and 95 % confidence interval of the differences in CRBSI rates and CRBSI admissions.
7. We will also perform a descriptive analysis identifying the most common microorganisms causing the CRBSI in the periods both before and during the SQ53 therapy.
8. We will also perform a survival analysis to plot a Kaplan-Meier curve

9. We will collect mortality data of patients. We will report an overall mortality, as well as, CRBSI-specific mortality in patients using SQ53 for CRBSI prevention.

Sample size and power calculation:

1. In the un-published study conducted in India SQ53 has been reported to reduce the CRBSI rate by 94%. We expect this effect size to be lower in our cohort. We performed our sample size calculation by utilizing the data reported in our previous study which reported CRBSI rates in high risk PN patients (Pre-ELT CRBSI rate= 3.53 and post-ELT 1.65 per 1,000 catheter days). Considering current CRBSI rate in our high-risk population to be 1.65 per 1000 catheter days, we will need a sample size of 46 patients to identify a 50% reduction in CRBSI rate with alpha of 0.05 and 80 % power.

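### The own-controls sub-analysis is not stated as a comparison between arms; read as a within-patient pre/post contrast, it shifts with the enrolled risk mix even if SQ53 does nothing

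*Combined protocol and SAP*

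**What the plan says.** All references are to the combined protocol and SAP.

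- **Data protection, processing and analysis of the data, item 4.** After the primary outcome (difference in CRBSI rate at 6 months), the plan adds: "We will also perform sub-analysis by utilizing patients as their own controls". It gives no arm, model, test or population for this. It refers to a timeline, but the Timeline section lists tasks and dates and does not mention the analysis. Item 6 names Poisson regression for comparing rates, without naming arm, period, baseline or offset terms.
- **Data collection, sample data sheet.** The columns include "Pre vs Post SQ53 trial enrollment" and "Number of Confirmed CRBSI in 6 months". Treatment and placebo patients each have a Pre and a Post row. Catheter-days are not on the sheet.
- **Blinding and Randomization.** The risk strata are defined as "High risk (1 or more CRBSI in previous 6 months) 2. Low risk (no CRBSI in previous 6 months"), plus New patients.
- **Inclusion criteria and patient recruitment, item 2c.** High risk has three routes here: "History of one or more CRBSI infection in the past 6 months"; "Immunocompromised state increasing the infection risk"; and "History of multiple catheter exchange in the past (greater or equal to 2 within the past 6 months) with difficult access". For the rest: "Patients who do not meet High-risk criteria will be classified as Low risk patients". New patients are those just started on PN, or on it for under 6 months without a CRBSI.

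**The concern.** The outcome in the pre-period is also what sorts patients into risk categories, and the six months before enrolment serve both purposes. Under either set of definitions, a Low-risk patient has no CRBSI in that window, and a New patient has a short or absent window with none in it. Every pre-period CRBSI therefore belongs to a High-risk patient, while post-period CRBSI can occur in all three categories. Counts in patients selected for a recent event tend to fall and counts in patients selected for having none can only hold or rise, whatever the wipe does.

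If the sub-analysis is run as a pre/post contrast within the SQ53 arm, its result mixes any effect of the wipe with the arm's risk composition. A reader could take a fall as support for SQ53, or take a flat result as evidence against it, when neither follows.

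**Working it through.** The plan gives no figure for this sub-analysis, so there is none to reproduce. The check asks what the contrast shows when the wipe is inert.

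**Inputs from the plan.** Six months, taken as 182.5 days; 1.65 and 3.53 per 1,000 catheter-days (Sample size and power calculation, item 1); 30 patients per arm (item 2).

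**Assumptions, none given in the plan.** 1.65 is used as the all-patient mean, although the plan attaches it to high-risk patients. Patient rates follow a gamma distribution with relative variance v = 0, 1, 2 or 4. New patients have 3 CRBSI-free pre-months. The High/Low/New mixes are illustrative.

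**Step 1: a bound without a frailty model.** One event in 182.5 days is 1,000/182.5 = 5.48 per 1,000. A patient classed High risk by CRBSI who then runs at 1.65 shows a fall of at least 1 − 1.65/5.48 = 70%; at 3.53, at least 36%. The trial is planned around a 50% reduction.

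**Step 2: expected counts per patient.** m = 1.65 × 0.1825 = 0.301.

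- P = P(pre ≥ 1) = 1 − (1 + vm)^(−1/v), or 1 − e^(−m) at v = 0
- Pre count given pre ≥ 1: m/P
- Post count given pre = 0: m/(1 + vm)
- Post count given pre ≥ 1: [m − (1 − P) × m/(1 + vm)]/P
- New, post count: m/(1 + vm/2)

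| v | 0 | 1 | 2 | 4 |
|---|---|---|---|---|
| P(pre ≥ 1) | 0.260 | 0.231 | 0.210 | 0.179 |
| Pre, given pre ≥ 1 | 1.158 | 1.301 | 1.434 | 1.679 |
| Post, given pre ≥ 1 | 0.301 | 0.533 | 0.727 | 1.054 |
| Post, given pre = 0 | 0.301 | 0.231 | 0.188 | 0.137 |
| Post, New | 0.301 | 0.262 | 0.231 | 0.188 |
| Apparent fall, CRBSI-selected | 74% | 59% | 49% | 37% |

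At 3.53 per 1,000 the fall is 53% / 37% / 29% / 20%. If half the High-risk patients enter by the other routes and have the pre = 0 rate, the High-risk fall at 1.65 is 48% / 41% / 36% / 29%; for v = 1, pre 1.301/2 = 0.651, post (0.533 + 0.231)/2 = 0.382.

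**Step 3: a whole arm, representative mix.** Take 20 established patients in the model's own proportions and 10 New. The established patients contribute 20m = 6.02 events before and after. For v = 1 the count ratio is (6.02 + 10 × 0.262)/6.02 = 1.43. On rates, the pre-period holds 20 + 10 × 0.5 = 25 patient-half-years against 30 after, so the ratio is multiplied by 25/30.

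- Raw counts, as on the sheet: 1.50 / 1.43 / 1.38 / 1.31
- Catheter-day rates: 1.25 / 1.20 / 1.15 / 1.09
- Without New patients: 1.00

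On rates, a true halving would show as 0.5 × 1.25 = 0.625 at v = 0, a fall of about 38%, and as a fall of about 45% at v = 4.

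**Step 4: an enriched mix, High/Low/New 15/8/7, all High risk by CRBSI.** For v = 1: pre 15 × 1.301 = 19.5; post 15 × 0.533 + 8 × 0.231 + 7 × 0.262 = 11.7; count ratio 0.60. The time factor is (23 + 3.5)/30 = 0.883.

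- Raw counts: 0.52 / 0.60 / 0.65 / 0.72
- Rates: 0.46 at v = 0, rising to 0.64 at v = 4

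This mix makes 15/23 = 65% of established patients High risk, about 2.5 to 3.6 times the model's share. The rate level matters too: at 3.53 and v = 0 the count ratio is 30 × 0.644/(15 × 1.356) = 0.95.

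**The case against.** **The within-arm reading is inferred.** Item 4 does not say that the contrast is confined to the SQ53 arm. The sheet holds what a between-arm comparison of change would need, and item 6 could be meant to cover it. This stands: a reader might infer that the plan commits to an uncontrolled pre/post claim, and the documents do not show that. They also nowhere specify the between-arm version, and own controls ordinarily means a within-patient contrast.

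**A reader might infer that the analysis will hide a real benefit.** The larger ratios (1.50 to 1.31) compare raw counts over unequal periods for New patients. The plan speaks of rates, and on rates the distortion is 1.25 to 1.09. It vanishes in a representative mix of established patients only. Strong masking is not supported.

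**A reader might infer that false positives are likely.** In 20,000 simulated null arms with mix 5/15/10 (exact two-sided conditional test of counts at 0.05), a significant fall appeared in 0.01% to 0.7% of arms. The 13% to 24% seen at 15/8/7 needs an enrichment that the plan does not suggest: letters go to every eligible patient, in alphabetical order.

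**A reader might add the loss of ethanol locks as a confounder.** The documents do not establish when the lock changed relative to each patient's two periods, or how large its effect would be. It forms no part of this point.

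**CRBSI is not the only High-risk route.** It is the only one in Blinding and Randomization, but one of three in the inclusion criteria. The forced pre-period event applies only to patients who qualify by CRBSI. The forced zero in Low-risk and New patients holds under both definitions.

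**Conclusion.** The point holds as a minor one. No section makes the own-controls sub-analysis a between-arm comparison, and on its ordinary reading it does not isolate an SQ53 effect. The direction of the bias follows from the category definitions alone: CRBSI-selected patients tend to fall, and Low-risk and New patients cannot fall.

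The net size in an arm cannot be fixed from the documents. Under the stated assumptions it runs from a spurious rise of 25% to 9% on rates (representative mix with New patients), through none (no New patients), to a spurious fall of 54% to 36% (enriched mix). These figures rest on an assumed rate level, frailty variance, enrolment mix and 3-month pre-period for New patients, and show dependence on mix rather than a forecast. The randomised 6-month comparison is not touched.

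**What to change.** In item 4, replace the own-controls sentence with a between-arm comparison of confirmed CRBSI after enrolment:

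- **All patients.** The Poisson model of item 6 with arm, log catheter-days as offset and overdispersion-scaled standard errors, adjusted for the randomisation risk category. New patients stay in through their own category.
- **Patients with a full 6-month pre-period.** A further between-arm version adjusted for the pre-period CRBSI count, or an arm-by-period term with standard errors clustered by patient.
- **Within-arm pre/post tables.** Descriptive only, with no p-value and no efficacy claim.

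The scaling is worth having. In 3,000 simulated null trials with 30 per arm and a model with arm, risk category and pre-period count, type I error over v = 0 to 4 reached 9.6% (5/15/10) and 10.5% (15/8/7) with model standard errors. With Pearson scaling it was 3.4% to 5.1% and 3.6% to 6.3%. That check used equal catheter-days, so it did not exercise the offset.

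**Cost.** A few sentences in item 4. Catheter-days per patient must come from the HPN database. New patients drop out of the pre-count version. At the illustrative rate about 60 × 0.301 = 18 events are expected under no effect, so few covariates can be carried.

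The two High-risk definitions, in the inclusion criteria and in Blinding and Randomization, should be reconciled as a separate point.

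### The planned Poisson comparison names neither stratification factor; this costs precision only with a dispersion-aware standard error and causes bias only if catheter-days differ by arm within risk groups

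*Combined protocol and SAP*

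**What the plan says.** Under Blinding and Randomization: "Stratification will be done on two factors: CRBSI risk category and catheter type". Three risk categories and two catheter types give six strata, with 1:1 allocation in blocks inside each. Block size is left to the home infusion pharmacy. Under Inclusion criteria and patient recruitment, item 3, the pharmacy receives both factors before it randomises.

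Under Data protection, processing and, analysis of the data, item 4 makes the primary outcome "differences in the CRBSI rate at 6 months after patient enrollments into the trial". Item 6 gives the model: "We will perform Poisson Regression analysis to compare the rates and 95 % confidence interval of the differences in CRBSI rates and CRBSI admissions". Item 8 adds: "We will also perform a survival analysis to plot a Kaplan-Meier curve". Neither item mentions risk category, catheter type, an offset or a variance method, and item 8 names no test or hazard ratio.

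The sample data sheet under Data collection has the column "Number of Confirmed CRBSI in 6 months" but none for catheter-days.

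**The concern.** Stratified allocation balances the arms on factors thought to drive CRBSI. An analysis usually carries those factors, for two reasons. First, if the error term is estimated from the spread between patients, it includes between-stratum variation that the design has already removed from the arm comparison; the interval is then too wide and the test falls below its nominal level. Second, if one arm loses more high-risk follow-up than the other, a crude rate ratio picks up that shift in case mix.

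The silence also leaves the model to be chosen after data have been seen, and the Timeline schedules an interim analysis.

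**Working it through.** **Inputs from the documents.** 30 patients per arm; 6 months (182.5 days) each; planning rate 1.65 per 1000 catheter-days; target rate ratio 0.5.

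**Assumed inputs.** The documents give no rates by stratum. Both 3.53 and 1.65 are high-risk figures in the sample size section, before and after ethanol lock; using them for different risk groups is purely illustrative. Unless stated otherwise: equal-sized risk groups and one catheter type at 1.5 times the rate of the other.

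**Planning figures.** The plan gives no figure for the effect of adjustment. Its enrolment reproduces as 46 × 1.3 = 59.8, or 60. Expected control events are 30 × 182.5 × 1.65/1000 = 9.03; with SQ53 at half that, 4.52; total 13.6. Whether 46 is adequate is a separate question.

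**1. Plain Poisson standard error.** For the log rate ratio it is √(1/D₁ + 1/D₀), where D₁ and D₀ are the events per arm. If counts are Poisson within strata, each arm's total is Poisson too, so differing stratum rates do not invalidate the formula when the arms are balanced. Simulation at 60 patients with rates 3.53/0.8/1.65:

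| Plain Poisson | Crude | Adjusted |
|---|---|---|
| SE, ratio 1 | 0.397 | 0.398 |
| Rejection, ratio 1 | 4.5% | 3.9% |
| Rejection, ratio 0.5 | 28.9% | 28.8% |

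**2. Dispersion-scaled standard error.** Without the factors, the estimated dispersion is about 1 + Var(μ)/mean(μ), where μ is a patient's expected count.

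- Rates 3.53/0.8/1.65, catheter multipliers 1 and 1.5: mean μ = 1.993 × 1.25 × 0.1825 = 0.455; Var(μ) = 0.0787; dispersion = 1 + 0.0787/0.455 = 1.17; SE factor √1.17 = 1.08.
- Rates 1.65/0.8/1.2, same multipliers: mean μ = 0.278; Var(μ) = 0.0096; dispersion 1.035; SE factor 1.02.

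Simulations at 60 patients, Pearson-scaled SE:

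| Scenario | SE crude / adjusted | Rejection at ratio 1, crude / adjusted |
|---|---|---|
| 3.53/0.8/1.65 (about 27 events at ratio 1) | 0.426 / 0.395 (8% wider) | 3.6% / 5.2% |
| Same mix, mean rescaled to 1.65 | about 7% wider | 3.4% / 5.1% |
| 1.65/0.8/1.2 | 0.530 / 0.524 (1% wider) | 3.1% / 2.9% |

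In the rescaled scenario, rejection at ratio 0.5 is 14.8% crude and 21.3% adjusted. Part of that gap arises because the adjusted scaled SE runs slightly small.

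A separate set used a 30/50/20% risk mix and a mean rate of 1.65. With a fourfold high-to-low ratio the scaled SEs at 60 patients were 0.513 and 0.481 (7% wider). With a tenfold ratio they were 0.546 and 0.467 (17% wider), but the actual spread of the adjusted estimate was 0.518, so much of that gap is the adjusted SE being too small. At 300 patients and tenfold, the crude robust SE was 0.241 against a true spread of 0.216 (12% too wide).

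**3. Variation between patients within a stratum.** At 60 patients, fourfold risk ratio and gamma dispersion 1, the plain Poisson type I error was 8.6% crude and 8.2% adjusted. Adjustment does not cure this; the variance method must.

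**4. Bias.** Take equal-sized risk groups at 3.53/0.8/1.65 and no true effect. The control rate is 5.98/3 = 1.993.

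- SQ53 loses 30% of its high-risk days: (0.7 × 3.53 + 0.8 + 1.65)/2.7 = 4.921/2.7 = 1.823; ratio 1.823/1.993 = 0.914.
- SQ53 loses 50%: 4.215/2.5 = 1.686; ratio 0.846.
- Both arms lose the same share: numerator and denominator are equal; ratio 1.00.

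Within each risk group the arms have the same rate, so a model with risk category and a catheter-days offset returns 1.00. Without the offset, the balanced model returns the ratio of counts, 4.921/5.98 = 0.82, with or without the factors.

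**The case against.** The best defence is that item 6 names plain Poisson regression and nothing else. A reader might infer that its interval is wrong because stratification is left out. Step 1 does not support that: for the model as named, crude and adjusted results are nearly identical. The precision argument starts only once a scaled or robust variance is brought in, and the plan mentions none. This stands. Such a variance is still a natural choice, because the sample data sheet itself illustrates a patient with two confirmed infections in 6 months.

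A reader might also infer that the plan has decided on a crude comparison. It has not; it is silent, and Poisson regression can carry covariates.

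A reader might infer that unequal catheter-days across risk groups bias the ratio. Under a common effect they do not, if the arms lose follow-up alike. Losses of 30% or 50% in one arm's high-risk group are assumptions. The documents give some route to unequal loss: only the SQ53 arm has the remote-site skin test, patients know their allocation, and 30% attrition is allowed for overall. They give no figure by arm or risk group.

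Finally, item 8 plans a plot, so no time-to-event test or interval can be called wrong.

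**Conclusion.** The point holds as a specification gap: the two factors that govern randomisation appear in no planned analysis. Under a plain Poisson standard error the omission has almost no effect. Under a robust or scaled one, the unadjusted interval is about 1% to 8% too wide at 60 patients in the moderate scenarios, and more with a tenfold difference in risk. At the planning rate the plain SE is √(1/9.03 + 1/4.52) = 0.576, so an 8% excess makes it 0.622. That is a modest loss beside the imprecision from about 14 events.

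The bias is conditional on loss of catheter-days that differs by arm within risk groups: 0.91 or 0.85 in the examples, removed by adjustment with an offset. Every size here depends on assumed stratum rates. The documents do not show that the planned interval is invalid or that the result will be biased.

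**What to change.** - In item 6, specify Poisson regression with arm, risk category (three levels) and catheter type (two levels) as randomised, main effects only, with log catheter-days as offset and a named dispersion-aware variance suited to a small sample. Keep the crude estimate as a sensitivity analysis.
- Reconcile the high-risk definition first. The recruitment section also counts immunocompromise and repeated catheter exchange; the randomisation section counts only CRBSI in the previous 6 months. The covariate must be the category actually used to randomise.
- Add catheter-days to the data sheet.
- State in advance how levels with no events will be merged. In the scenario rescaled to 13.6 events, a risk or catheter level had none in about 20% of simulated trials.
- Add a stratified log-rank test only if a time-to-event test is added to item 8.

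**Cost.** Mostly wording plus one data field, since both factors are known before randomisation. The model spends three extra degrees of freedom on about 14 events. A scaled SE can run slightly small after adjustment, and adjustment alone does not deal with overdispersion within strata.
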